#### 3.3 Intervention

#### Frontend design

The MindCraft app is designed with a modular and adaptable framework to facilitate future improvements, support different study questions and provide customisation options to meet individuals' needs and favour engagement (Kadirvelu et al., 2023). The MindCraft app is not classed as a medical device and is not CE-marked. The MindCraft app will be used as a research tool only, and we do not intend to commercialise the app in the future. The key modular components include:

- 1. Customisable active questions: MindCraft allows users to select daily active questions tailored to their unique mental health objectives. Participants are free to select among 8 required and 11 optional trackers.
- 2. Configurable passive data: users can choose which passive data they wish to share, ensuring that they have control over their privacy. The passive trackers include phone and app usage, battery level, location (collected when there is a significant change in the user's location), steps, background noise (collected only when the app is in the foreground) and ambient lighting.

Users can set their active and passive data sharing preferences during the initial onboarding process and can also modify them at any time through the app's settings. MindCraft app is available for free download from the Apple Store and Google Play Store. A valid study ID code is required to use the app (Figure 3). The MindCraft app comprises 3 main tabs in its User Interface: the main tab, the progress tab, and the settings tab (Figure 4)

[figure not shown]

Figure 3. Login screen.

[figure not shown]

Figure 4. Main Tab and Progress Tab.

 Main tab (Figure 4): The app incorporates visual representations of users' mood and mental well-being markers, which have been shown to increase engagement. The main tab is the first view of the app when launched by a registered user. Here, the user can self-report a questionnaire related to their mood and well-being. The questionnaire contains 8 required questions (sleep quality, sleep quantity, mood, motivation, anxiety, loneliness, appetite, and

exercise), as well as 11 additional questions (racing thoughts, negative thinking, hopefulness, headaches, irritability, confidence, sociability, energy levels, productivity, self-care, leisure, and a custom metric called "your measure"). The user can manage the optional questions through the settings tab. Each question can only be answered once a day; thus, the question will disappear after each submission. Most of the self-reported questions (such as mood and sleep quality) are on a scale of 1-7 and contain a slider. Other questions (such as sleep quantity and exercise time) collect numerical data from text boxes, and the input is type-checked to ensure only valid inputs are stored (e.g., numerical numbers and not text).

 Progress tab (Figure 4): The progress tab charts the self-reported updates given by the user throughout the study. Selecting the data of interest causes the graph view to display the historical data and the average score for the selected period.

[figure not shown]

Figure 5. Settings Tab.

Settings tab (Figure 5): In the settings tab, the user can manage the active and passive data settings, read the privacy policy, and withdraw from the study. The app allows the user to enable or disable the optional active data questions that are most relevant to them. The "Help" option under the Settings tab allows users to seek support when needed. To facilitate this, MindCraft lists four external organisations: Shout, YoungMinds, Best For You NHS, and Kooth - along with a brief description of each organisation and links to their websites.

Personalised digital Al-based recommendations (experimental intervention group) The experimental arm will deliver personalised behavioural recommendations (Al nudges) via the MindCraft mobile app (Figure 6). This reinforcement learning

recommendation system (Figure 1) personalises and dynamically delivers digital Al nudges based on user mental health states (as measured by active and passive trackers) and ratings of the nudges to improve mental health and well-being.

For example, participants self-reporting low mood and/or low step count might be nudged to "take a walk outside". Then, if participants rate this nudge positively, they will be provided with similar recommendations in the future. However, if they rate the nudge negatively because, for example, they do not like walking (and maybe prefer different forms of exercise), they will receive different future nudges, such as "do some light stretching".

Non-personalised digital self-help using generic CBT principles (active control group) The active control will be non-personalised digital self-help recommendations based on generic principles derived from cognitive behavioural therapy (CBT) (general nudges). These will include tips, advice, strategies and psychoeducation on behavioural activation. Recommendations will be delivered via the MindCraft app, using the same format as the personalised AI recommendations, to make the interventions appear similar.

#### Self-monitoring only (control group)

The control will consist of self-monitoring through the MindCraft app and usual practice. Self-monitoring will include daily ratings and charts of active trackers. Usual practice, as received by the young person outside the trial, may include no provision of intervention, local provision of intervention, support from a GP, local health services or youth services, or provision of intervention within the school.

[figure not shown]

Figure 6. Examples of nudges.

Researchers can also access an administrator dashboard (Figure 7) to track the usage of the app by the participants. The dashboard allows the researchers to easily

track the engagement of users and oversee the general performance of the algorithm via the star rating feedback for the nudges.

[figure not shown]

Figure 7. Administrator dashboard.

#### 3.4 Recruitment and Study Setting

We will recruit CYP in years 10 to 13 (age 14-19) attending schools in the United Kingdom. We aim to recruit around 5-10 schools, depending on how many students they accommodate. The research team will reach out to schools via email to the school principal/school staff and send information about the study. The research team will offer schools the option to learn more about the research and participate in educational activities related to mental health and digital interventions as part of the mandatory Social and Emotional Aspects of Learning (SEAL) framework.

### 3.5 Screening and Consent Procedures

Potential participants will be informed about the study by their school. If data collection is carried out remotely, teachers will distribute information about the study via email to students and parents/guardians. Teachers will also send students a link to a Consent to Contact online form, where they will be asked to include their contact details and those of parents/guardians. On first contact with the students, the lead researcher ([name]) will email the full Participant Information Sheet and Consent/Assent Form to the students. Students over 16 will sign the Consent Form and email it back to the researcher. For any young person under 16, we will obtain informed parental consent by using opt-out consent (see Consent). The researcher

will send the Opt-out Consent Form to parents/guardians. Parents/guardians will sign and email back the Opt-out Consent Form to the researcher if they do not wish their child to participate. Parents will have at least two weeks to complete the opt-out form before any data is collected from children. Participants under 16 years old will also be required to provide written assent by signing the Assent Form and emailing it back to the researcher.

Alternatively, if the school prefers to carry out data collection in person on school premises, teachers will circulate the Participant Information Sheet to students and Parent/Guardian Information Sheet and Opt-out Consent Form for parents/guardians via email at least two weeks before the day of data collection. Students over 16 years old will provide informed consent electronically via Qualtrics on the day of data collection. They will also be asked to include their contact details and those of their parents/guardians. For participants under 16 years old, consent from a parent/guardian will be required for participation. Parents/guardians will sign and email back the Opt-out Consent Form to the researcher if they do not wish their child to participate. Parents will have at least two weeks to complete the opt-out form before any data is collected from children on school premises. Participants under 16 years old will provide written assent online via Qualtrics on the day of data collection.

Participants will be followed up at 1 month. If data collection is carried out remotely, baseline and follow-up measures will be collected via an online Qualtrics questionnaire sent to the participant's email. If data collection is carried out in person, participants will complete the baseline (and follow-up) questionnaires through a Qualtrics link (separate from the Consent Form) on their mobile phones.

Completion of the baseline and outcome assessments should take a maximum of 30 minutes. No identifiable information will be collected. Participants will be assigned a unique participant ID, which they will use to complete the baseline and follow-up assessments and sign in to the study app (see Data Management section). Based on their ID, participants will be randomised to different versions of the MindCraft app (see Randomisation).

Reimbursement will be provided upon completion of the study, with the mode of reimbursement determined by each participating school. Schools may choose to distribute vouchers to students or receive the funds centrally to support researchand mental health—related activities, such as travel for workshops at Imperial.

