### 3.12 Risks and Risk Management

There are no foreseeable serious risks associated with this project. Participants' well-being and safety will be considered a priority concern at all points in the study. However, theoretically, it is possible that a number of procedures (listed below) included in the study may result in (i) revealing elevated mental health risk or (ii) causing increased levels of distress.

If this is the case, the necessary steps to guarantee the participant's well-being and safety will be taken as described below. We will follow Imperial College London's Safeguarding policy.

Study procedures that may result in increased perceived distress include:

- Responding to questionnaires during baseline and outcome assessments
- Self-reporting data and mental health monitoring through the MindCraft app
- Cognitive/behaviour change following MindCraft app use and nudges recommendations

The risk (i), i.e. of revealing elevated mental health risk as measured by high SDQ scores at baseline, will be addressed by putting in place the following series of procedures:

- If the presence of elevated mental health risk is disclosed, the participant will be signposted to specific support resources on managing poor mental health including those to manage suicidal thoughts (https://patient.info/mental-health/depression-leaflet/suicidal-thoughts), as well as additional external sources of support, which will include those listed in the Help section of the MindCraft app (i.e. Shout, YoungMinds, Best For You NHS, and Kooth).

We will also offer participants the option of being contacted by clinicians part of the research team. In case of disclosure of actual or intended harm, in order to protect the immediate safety of the participant, the participant's parents/guardians will be informed by the lead researcher ([name]) via email or phone call. The contact details of the parents/guardians will be provided on the consent-to-contact form.

 In case participants choose to be contacted by the research team, they will be informed that all information is confidential. The limits of confidentiality (e.g. that the researcher may have an ethical duty to disclose information to a third party to protect the immediate safety of the participant or someone else in the rare

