#### 7.2. CONSENT

Potential participants will be informed about the study by their school. If data collection is carried out remotely, teachers will distribute information about the study via email to students and parents/guardians. Teachers will also send students a link to a Consent to Contact online form, where they will be asked to include their contact details and those of parents/guardians. On first contact with the students, the lead researcher ([name]) will email the full Participant Information Sheet and Consent/Assent Form to the students. Students over 16 will sign the Consent Form and email it back to the researcher. The Consent Form, signed by both participant and researcher, will be emailed back to the participant.

For any young person under 16, we will obtain informed parental consent by using opt-out consent (see below). The researcher will send the Opt-out Consent Form to parents/guardians via email along with a Parent/Guardian Information Sheet, which gives a full description of what children are expected to do and how participant data are stored. Parents/guardians will sign and email back the Opt-out Consent Form to the researcher if they do not wish their child to participate. Parents will have at least two weeks to complete the opt-out form before any data is collected from children. The Opt-Out Consent Form, signed by both the parent/guardian and researcher, will be emailed back to the parent/guardian. Participants under 16 years old will also be required to provide written assent by signing the Assent Form and emailing it back to the researcher. The Assent Form, signed by both participant and researcher, will be emailed back to the participant.

All participants will be told that participation is voluntary, and they may withdraw at any point without giving a reason. All Forms (Consent Form, Assent Form, Opt-out Consent Form) will be stored in an Imperial College London secure OneDrive.

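### In the remote route, the parental opt-out form for under-16s apparently depends on contact details the pupil enters, with no check of receipt, and harm alerts rely on the same details

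*Protocol*

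**What the plan says.** Sections 3.5 and 7.2 of the protocol describe two recruitment routes.

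**Remote route.** Teachers email study information to students and parents. The pupils, not the parents, then receive a Consent to Contact form, and it is the pupils who fill in both sets of details: the form is the place "where they will be asked to include their contact details and those of parents/guardians". For under-16s the parent documents come from the research team: "The researcher will send the Opt-out Consent Form to parents/guardians via email along with a Parent/Guardian Information Sheet". A reply is needed only to refuse: "Parents/guardians will sign and email back the Opt-out Consent Form to the researcher if they do not wish their child to participate". The waiting time is fixed: "Parents will have at least two weeks to complete the opt-out form before any data is collected from children". The pupil must also give written assent.

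**In-person route.** Here teachers circulate the parent documents themselves, including the "Opt-out Consent Form for parents/guardians via email at least two weeks before the day of data collection".

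**Harm disclosure.** Section 3.12 says the lead researcher informs parents by email or phone if a participant discloses harm or an intention to harm. It names the source of the details: "The contact details of the parents/guardians will be provided on the consent-to-contact form".

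**The concern.** An opt-out scheme protects a minor only if the parent is actually offered the chance to refuse. In the remote route that chance appears to depend on the pupil having entered a working, genuine parent contact. If the entry is mistyped or false, the parent never sees the form, no refusal comes back, and the pupil proceeds on assent alone. Nothing in the described procedure would reveal this. Sections 3.5 and 7.2 nevertheless call the result informed parental consent.

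The baseline battery asks about self-harm, substance use, eating disorder symptoms and sexual orientation, and the app can collect location. These are matters on which a parent of a 14- or 15-year-old might wish to decide. The harm alert draws on the same pupil-supplied details, so the two parental safeguards can fail together.

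**Working it through.** No arithmetic applies and the protocol gives no figure to reproduce. The check is to follow an under-16 through each route and see where a parent could be missed.

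| Step | Remote route | In-person route |
|---|---|---|
| First email to parents | Teachers; study information only, opt-out form not named | Teachers; parent information sheet and opt-out form |
| Who sends the opt-out form | Researcher, after the pupil is contacted | School |
| Source of the parent contact | Only source described: the form completed by the pupil | Not stated; teachers do the mailing, independently of any pupil form |
| What stops enrolment | A returned form | A returned form |
| Check of address or receipt | None described | None described |
| Pupil's own step | Written assent | Written assent |

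Four things follow for the remote route.

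1. *Where the form goes.* No single sentence says that the researcher uses the parent contact from the Consent to Contact form. That reading rests on two facts: no other source of parent details is given to the researcher, and section 3.12 says parent details come from that form. It is a strong inference, not stated text.
2. *What a failed delivery does.* Because only a refusal is returned, a parent who agrees and a parent who was never reached look the same to the researcher. Two weeks later both pupils may be enrolled on their own assent.
3. *Whether the teachers' email closes the gap.* It may alert some parents that the study exists. It is not said to carry the form or to explain how to opt out. It reduces the risk without removing it.
4. *What else depends on the entry.* The harm alert uses details from the same form. It may be made by phone as well as email, so an error in the email address alone need not defeat it. A wrong or false parent entry as a whole can defeat both the opt-out and the alert.

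The difference between the columns that matters is who sends the opt-out form. Both routes keep opt-out consent. Only the remote route appears to pass the form through pupil-supplied details, and the protocol gives no reason for the difference.

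**The case against.** The strongest reply is that opt-out consent was a deliberate choice. Section 7.2 argues for it on grounds of participation and representation of disadvantaged pupils, and section 7.1 reports ethics approval. Any opt-out scheme treats silence as non-refusal. This stands, and the point does not dispute opt-out. Those arguments do not, however, explain why the form should reach parents by a less secure path in one route than in the other.

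It can also be said that other layers exist. The school emails parents in the remote route too, under-16s must assent in writing, and section 4.2 requires that they can seek parental consent. After a harm disclosure, section 3.12 also offers signposting and optional contact with clinicians. These soften the defect. None of them shows that a parent received the means to refuse.

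Three stronger readings are tempting and are not supported.

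- *That taking contact details early breaks the two-week rule.* In section 3.5 data collection refers to the baseline and follow-up questionnaires. Contact details taken for recruitment are not study data in that sense, so there is no contradiction.
- *That unread email is a fault of the remote route.* A parent can leave a teacher's email unread just as easily. The specific weakness is a wrong or false entry by the pupil.
- *That randomised participants would be lost from the intention-to-treat analysis.* Nothing in the protocol says such records would be removed.

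Reliance on pupil-supplied details for harm alerts is also not confined to the remote route: in-person students over 16 are asked to enter their parents' details as well. The weakness in the consent step is specific to the remote route.

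**Conclusion.** The concern holds in this form: as written, the remote route has no described means of telling a parent who agreed from one who was never reached, and the contact details apparently come from the child. The harm alert depends on the same entry.

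The conclusion rests on one inference, that the researcher uses the Consent to Contact details to send the opt-out form. If the school supplies parent addresses to the researcher in practice, the consent part falls away once the protocol says so, and the harm-alert part remains.

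The group exposed is the under-16s recruited remotely. Its size, and the share with a wrong entry, cannot be derived from the protocol, and any headcount would be a product of assumptions. A change is still worthwhile because the affected group are minors, the failure would go unnoticed, and the protocol already contains the better procedure.

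**What to change.** In sections 3.5 and 7.2, for the remote route, have teachers send the Opt-out Consent Form and the Parent/Guardian Information Sheet with the email they already send to parents, as in the in-person route. Start the two-week period from that email. Parents would still return a refusal to the researcher.

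The cost is two attachments and an ethics amendment. Design, sample size and analysis do not change.

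As an optional addition, the school could confirm the parent contact held for harm alerts. That takes some staff time, which section 7.2 seeks to spare, and it tells the school which pupils volunteered. The investigators should weigh those costs; the main fix does not depend on it.

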### 3.6 Baseline and Follow-Up Assessments

The baseline assessment consists of web-based self-reported validated mental health measures and demographic information (see Outcomes):

- Screening Measures: Mood Disorder Questionnaire (MDQ); Screening to Brief Intervention (S2BI). MDQ and S2BI questionnaires will be used to characterise the sample.
- Primary Outcomes: Strengths and Difficulties Questionnaire (SDQ)

- Secondary Outcomes: Eating Disorders Diagnostic Scale (EDDS); Sleep Condition Indicator Questionnaire (SCI); Self-Injurious Thoughts and Behaviours Interview (SITBI); Self-Efficacy Questionnaire for Children (SEQ-C); World Health Organisation- Five Well-Being Index (WHO-5)
- Demographics: age, gender, sexual orientation, ethnicity, education level, socioeconomic status, location (school)
- Presence of learning difficulties, organic brain disease, or severe neurological impairment that prevents independent use of smartphone app (yes/no)

#### 3.7 Outcome Measures

#### Screening measures

- The Mood Disorder Questionnaire (MDQ) (Hirschfeld et al., 2000) is a screening instrument for bipolar disorder. The MDQ includes 13 questions plus items assessing symptoms and functional impairment. A total score is calculated where a "Yes" provides a score of 1 and "No" is 0. To meet the threshold for bipolar disorder, respondents need to have a score of 7 or more for questions 1-13, "yes" for symptoms clustered in the same time period and symptoms causing either "moderate" or "serious".
- The Screening to Brief Intervention (S2BI) is a brief screening tool developed by the National Institute on Drug Abuse (NIDA) to assess for substance use disorder risk among adolescents 12-17 years old (NIDA, 2019). S2BI ask respondents about the frequency of past-year use of tobacco, alcohol, marijuana, unprescribed prescription drugs, illegal drugs, inhalants and herbs/synthetic drugs. According to their responses ("Never", "Once or twice", "Monthly", "Weekly or more"), this tool triages respondents into one of three levels of substance use disorder risk: no reported use, lower risk and higher risk. The questionnaire has been validated in adolescent samples (Kelly et al., 2014).

